8.1.6 Unexpected Adverse Events

The Sponsor will assess all SAEs whether they are expected or unexpected. An unexpected AE is any adverse drug event, the outcome, specificity, or severity of which is not consistent with those noted in the Reference Safety Information section of the current IB.

8.1.7 Causality Assessments

All AEs (including SAEs) will be assessed by the Investigator and Sponsor for the causal relationship of the AE to the study drug using the following definitions described in [Table 7](#).

For reporting and data analysis purposes, AEs reported with a causality assessment of "Definitely", "Probably", and "Possibly" are to be considered as "having a reasonable causal relationship" to study drug. In case of disagreement between the Investigator and the Sponsor, the more conservative assessment will determine the reportability of the case.

Table 7: Relationship to Study Drug

	Relationship	Description
1	Not related	This category applies to those AEs which, after careful consideration, are clearly and incontrovertibly due to extraneous causes (disease, environment, etc.).
2	Unlikely (must have 2)	In general, this category can be considered applicable to those AEs which, after careful medical consideration at the time when they are evaluated, are judged to be unrelated to the study drug. An AE may be considered unlikely if or when: 
 1. It does not follow a reasonable temporal sequence from administration of the test drug. 2. It could readily have been produced by the subject's clinical state, environmental or toxic factors, or other modes of therapy administered to the subject. 3. It does not follow a known pattern of response to the test drug. 4. It does not reappear or worsen when the drug is re-administered.
3	Possibly (must have 2)	This category applies to those AEs for which, after careful medical consideration at the time they are evaluated, a connection with the test drug administration appears unlikely but cannot be ruled out with certainty. An AE may be considered possibly related if or when: 
 1. It follows a reasonable temporal sequence from administration of the test drug. 2. It could not readily have been produced by the subject's clinical state, environmental or toxic factors, or other modes of therapy administered to the subject. 3. It follows a known pattern of response to the test drug.
4	Probably (must have 3)	This category applies to those AEs for which, after careful medical consideration at the time they are evaluated, are felt with a high degree of certainty to be related to the test drug. An AE may be considered probably related if or when: 
 1. It follows a reasonable temporal sequence from administration of the test drug. 2. It could not be reasonably explained by the known characteristics of the subject's clinical state, environmental or toxic factors, or other modes of therapy administered to the subject. 3. It disappears or decreases on cessation or reduction in dose. There are important exceptions when an AE does not disappear upon discontinuation of the drug, yet drug-relatedness clearly exists (eg, bone marrow depression, fixed drug eruptions, tardive dyskinesia). 4. It follows a known pattern of response to the test drug.
5	Definitely (must have all)	This category applies to those AEs which the Investigator feels are incontrovertibly related to test drug. An AE may be assigned an attribution of definitely related if or when: 
 1. It follows a reasonable temporal sequence from administration of the test drug. 2. It could not be reasonably explained by the known characteristics of the subject's clinical state, environmental or toxic factors, or other modes of therapy administered to the subject. 3. It disappears or decreases on cessation or reduction in dose with re-exposure to drug. (Note: this is not to be construed as requiring re-exposure of the subject, however, a category of definitely related can only be used when a recurrence is observed.)

	Relationship	Description
		4. It follows a known pattern of response to the test drug.

AE = adverse event.

8.2 Reporting Serious Adverse Events and Adverse Events of Special Interest

Investigators must report SAEs which are related to study procedures and occur during prescreening and SAEs/adverse events of special interest (AESIs) occurring from the time the subject signs the Main ICF up to 30 days after the last administration of AFM24 or until the start of a new anti-cancer treatment, whichever is sooner, to the Sponsor or delegate within 24 hours of becoming aware of the event, by entering all required information in to the Electronic Data Capture (EDC) system by completing an electronic Case Report Form (eCRF) in accordance with the eCRF completion guidelines. Upon completion of the eCRF and submission of the eCRF, an automated notification will be triggered and will be received by the safety service provider and Sponsor.

In the unlikely event of a malfunction of the eCRF, sites are provided with paper-based SAE/AESI reporting forms; forms will be completed by the study Investigator and e-mailed within 24 hours to [contact]. The Investigator shall ensure that the information is entered in the eCRF as soon as the eCRF technical issues are resolved.

(Note: Any SAEs that are related to study procedures and occur during pre-screening and any SAEs that occur following signing the Main ICF and prior to the first dose of study drug will still be reported using the SAE form).

Other supporting documentation of the event may be requested by the Sponsor or delegate and should be provided as soon as possible in an anonymized manner. Follow-up information about a previously reported SAE/AESI must be reported within the same applicable timeframe of receiving it. All SAEs/AESIs will be followed up until resolution or stabilization at a level acceptable to the Investigator and/or the Sponsor.

The Investigator is not responsible for actively seeking new SAEs after the follow-up period; however, if the Investigator becomes aware of an SAE that is reasonably associated with study treatment after the study period including follow up, this must be reported to the Sponsor.

8.3 Other Important Events for Immediate Reporting

Adverse events meeting the following criteria, although not categorized as ‘serious’ per International Council for Harmonisation (ICH) definition, are reportable to the Sponsor in the same timeframe as SAEs to meet certain local requirements and the study needs:

- A new cancer (that is not a condition of the study);
- A reported pregnancy or lactation after receipt of study drug and for ≤ 60 days from last dose; and
- An overdose (defined as a dose of AFM24 which is $\geq 10\%$ above the intended daily dose or a dose interval < 4 days between 2 consecutive doses).

Such events must be reported within 24 hours to the Sponsor either by electronic report or paper.

8.3.1 Adverse Events of Special Interest

Infusion-Related Reactions

The occurrence of IRRs is within the anticipated safety profile of AFM24, considering experiences with other EGFR and CD16 targeting agents.

Infusion-related reactions can manifest with allergic or anaphylactic symptoms, including but not limited to chills, flushing, hypotension, fever, hypoxia, loss of consciousness, bronchospasm, and even cardiac arrest. Although the majority of such IRRs are mild to moderate, in some rare cases these can be life threatening or even fatal. Most of the IRRs are associated with the first infusion (during or shortly after the infusion); however, IRRs can happen during or after any infusion, despite the lack of previous signs or symptoms. In the nonclinical studies of AFM24, there were no signs of IRRs or anaphylactic symptoms.

In order to increase the understanding of IRRs, these events are considered to be AESIs. This means:

- Any of these events should be reported within 24 hours of occurrence.
- The SAE form should be used.
- All symptoms suggesting an IRR should be mentioned.

Of particular interest is information related to the timely development of symptoms relative to dose per time, actions taken as well as outcome of events.

The data will not be subject to reporting to Independent Ethics Committee (IEC)/Independent Review Board (IRB)/Regulatory Authorities unless such an event qualifies as SAE.

8.3.2 Exposure During Pregnancy or Lactation

Pregnancy and breastfeeding are considered exclusion criteria for this study (Section 4.2). Although pregnancy and lactation are not considered AEs, it is the responsibility of Investigators or their designees to report any pregnancy or lactation in a subject (spontaneously reported to them) or pregnancy in a subject's partner that occurs during the study. Immediately discontinue AFM24 treatment permanently in case of pregnancy.

Pregnancies and lactations that occur in subjects after the ICF is signed but before starting study drug must be reported by the Investigator if they cause the subject to be excluded from the study. Pregnancies and lactations that occur in a study subject or a pregnancy in a subject's partner from the time of first study drug through to 60 days following cessation of AFM24 study drug, must be reported by the Investigator. All reported pregnancies must be followed to the completion or termination of the pregnancy. If the pregnancy continues to term, the outcome ie, the health of the infant, will be requested by the Sponsor. Parental and neonatal outcomes must be recorded even if they are completely normal and without AEs. Offspring should be followed up for at least 8 weeks after delivery. Longer observation periods may be determined by the Sponsor if an adverse outcome of the pregnancy was observed.

Such events must be reported within 24 hours to the Sponsor via email, fax, or telephone. The reporting procedures can be found in the SAE completion guidelines located in the Study Operations Manual (or equivalent).

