and up to 6 subjects. Dose escalation will be guided by an adaptive Bayesian logistic regression model (BLRM) following the dose escalation with overdose control (EWOC) principle. This design uses all accumulating toxicity data to assign enrolling subjects to doses that have a higher chance of targeted toxicity (close to the MTD), while controlling the risk of excessive toxicity. To further ensure safety, the safety findings of each cohort will be carefully reviewed by the Safety Review Committee (SRC) prior to dose escalation decisions for the subsequent dose cohort.

During Phase 1, if a subject is tolerating AFM24 without significant evidence of disease progression or AFM24-related toxicity, the subject may, beginning with Cycle 3 or a subsequent cycle, have the dose increased to a dose that has already been established as tolerable by the SRC, and with the agreement of the SRC. This intra-subject dose escalation may allow subjects a greater possibility of benefit from treatment with AFM24 than might be achieved at the starting dose in his/her assigned dose cohort.

Risks of the tumor biopsy (mandatory for the subjects in the dose escalation phase [Phase 1]) include pain and tenderness at the tumor biopsy site and potential bleeding complications, which will be minimized by inclusion of subjects who have at least 1 site of tumor that is accessible to biopsy and that is considered by the Investigator to be low risk and of sufficient size to undergo a biopsy procedure, and monitoring per institutional practice.

No reproductive toxicity or carcinogenicity studies have been conducted with AFM24 to date. Both women and men should be fully informed of the lack of reproductive toxicity testing. Women of childbearing potential and men must agree to use adequate contraception from 14 days prior to the first dose of study drug up to 120 days after the last dose of study drug. Women must have a negative pregnancy test within 7 days prior to first dose of AFM24. It is unknown whether the drug is excreted in human milk, and women who are breast feeding are excluded from the study.

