- Cohort B: Subjects with ccRCC whose disease has progressed after having received ≥ 1 prior line(s) of therapy, which must have included a TKI (eg, sunitinib, pazopanib) and a checkpoint inhibitor (eg, pembrolizumab, avelumab, nivolumab).
- Cohort C: Subjects with advanced or metastatic NSCLC harboring a targetable EGFR kinase domain mutation and whose disease has progressed on or after having received ≥ 1 prior lines of therapy for advanced disease including ≥ 1 prior TKI approved for EGFR mutated NSCLC, such as gefitinib, erlotinib, afatinib, dacomitinib, or osimertinib. Subjects who were treated with a 1st or 2nd generation TKI in 1st line and developed a documented T790M mutation must have received a TKI targeting this mutation such as osimertinib or lazertinib to be eligible. Subjects must have documentation of EGFR mutated NSCLC as assessed by an approved test using genomic sequencing of tumor or circulating free tumor DNA.

12) Female subjects must have a negative urine or serum pregnancy test within 7 days prior to first dose of AFM24 if of childbearing potential or be of non-childbearing potential. If the urine pregnancy test is positive or cannot be confirmed as negative, a serum pregnancy test will be required. The serum pregnancy test must be negative for the subject to be eligible. Non-childbearing potential is defined as:

- Postmenopausal, defined as no menses for 12 months without an alternative medical cause. A high follicle-stimulating hormone (FSH) level in the postmenopausal range may be used to confirm a post-menopausal state in women not using hormonal contraception or hormonal replacement therapy. However, in the absence of 12 months of amenorrhea, a single FSH measurement is insufficient.
- Surgically sterile. Surgical sterilization methods include hysterectomy, bilateral salpingectomy, and bilateral oophorectomy.

13) Females of childbearing potential must agree to sexual abstinence (defined below) or be willing to use a highly effective method of contraception for the course of the study from 14 days prior to the first dose of study drug through 120 days after the last dose of study drug. Acceptable highly effective birth control methods include:

- Oral, intravaginal, or transdermal combined (estrogen and progestogen containing) hormonal contraception associated with inhibition of ovulation;
- Oral, injectable, or implantable progestogen-only hormonal contraception associated with inhibition of ovulation;
- Intrauterine device;

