- Intrauterine hormone-releasing system;
- Bilateral tubal occlusion;

- Vasectomized partner (provided that partner is the sole sexual partner of the female of reproductive potential and that the vasectomized partner has received medical assessment of the surgical success); and
- Sexual abstinence. In the context of this study, sexual abstinence is considered a highly effective method only if defined as refraining from heterosexual intercourse from 14 days prior to the first dose of study drug up to 120 days after the last dose of study drug. The reliability of sexual abstinence needs to be evaluated in relation to the duration of the clinical study and the preferred and usual lifestyle of the subject.

14) Males who have female partners of childbearing potential must agree to use a highly effective method of contraception as described in inclusion criterion 13, starting with the first dose of study drug through 120 days after the last dose of study drug.

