- 15) Subjects who require systemic steroid treatment or any other immunosuppressive therapy, or subjects who received such therapy within 4 weeks prior to the first dose of study drug, with the exceptions as outlined under exclusion criterion #13).
- 16) Pregnant, breastfeeding, or expecting to conceive or father children within the projected duration of the study, starting with the Screening visit (females) or first dose of study drug (males) through 120 days after the last dose of study drug.

- 17) Subject's unwillingness to comply with the protocol or inability to appreciate the nature, meaning, and consequences of the study and to formulate his/her own wishes correspondingly.
- 18) Any medical, psychological, or social condition that would interfere with the subject's participation in the study.

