7.2.2 Pregnancy and FSH tests

Female subjects of reproductive potential will have a pregnancy test carried out at Screening and at time points specified in the SoA tables (APPENDIX A [Section 14.1] and APPENDIX B [Section 14.2] for weekly and q2w, dosing regimens, respectively). This test must be carried out within 7 days prior to first AFM24 administration. A urine test is acceptable; however, where a urine test is equivocal, a blood test must be performed to confirm the result. Subjects confirmed as pregnant will be excluded from participation in the clinical study.

Female subjects of reproductive potential with a negative pregnancy test at screening will continue to have pregnancy tests conducted at least every 4 weeks during the study and at the End of Treatment visit.

Female subjects who require documented confirmation of post-menopausal status will have their FSH levels assessed at Screening. Where post-menopausal status is not confirmed, subjects will be required to undergo pregnancy testing per protocol to confirm suitability to proceed.

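### Pregnancy and lactation reporting has a stated limit of 60 days after the last dose, half the 120-day contraception period, and the protocol does not say whether this limit or a broader duty governs

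*Protocol*

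**What the plan says.** **Reporting limit.** Section 8.3.2 obliges the investigator to report a pregnancy or lactation in a subject, or a pregnancy in a partner, arising "from the time of first study drug through to 60 days following cessation of AFM24 study drug". Section 8.3 lists "A reported pregnancy or lactation after receipt of study drug" among the events for immediate reporting and applies the same 60-day limit.

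**General duty.** The opening paragraph of 8.3.2 makes sites responsible to "report any pregnancy or lactation in a subject (spontaneously reported to them") and to report partner pregnancies, for events during the study. It gives no day limit.

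**Contraception and no-conception period.** Inclusion criterion 13 requires contraception or abstinence in women of childbearing potential "from 14 days prior to the first dose of study drug through 120 days after the last dose of study drug". Criterion 14 requires contraception in men with partners of childbearing potential "starting with the first dose of study drug through 120 days after the last dose of study drug". Exclusion criterion 16 excludes pregnancy, breastfeeding and plans to conceive or father a child "through 120 days after the last dose of study drug". Section 1.8 gives the same 120 days and states: "No reproductive toxicity or carcinogenicity studies have been conducted with AFM24 to date".

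**Detection.** Under section 7.2.2, women of reproductive potential "will continue to have pregnancy tests conducted at least every 4 weeks during the study and at the End of Treatment visit". No later test is scheduled. Section 3.9 and the schedules in Appendices A and B limit the long-term follow-up contact to subsequent therapies, disease status and survival.

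**The concern.** The sponsor treats the 120 days after the last dose as a period in which conception should be avoided, but the explicit duty to report a conception ends halfway through it. Section 8.3.2 refers to section 4.2 for the pregnancy exclusion, where the period is 120 days, and then sets 60 days for reporting without giving a reason. The 60-day figure appears in two sections, so it is not an isolated slip.

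The general duty in 8.3.2 may reach later cases, but its relation to the 60-day limit is not stated. One site could report a pregnancy that began on day 80 and another could decline to, each relying on the text.

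The consequence lies in follow-up. Section 8.3.2 requires reported pregnancies to be followed to their end, normal outcomes to be recorded, and offspring to be followed for at least 8 weeks. A pregnancy that is not reported gets none of this. With no reproductive toxicity studies, such outcomes are an important source of information.

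**Working it through.** No sample size, power or error rate is involved. The check compares the stated windows and places the scheduled contacts on the same time axis, in days after the last dose.

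**Inputs**
- Explicit reporting limit: 60 days (8.3, 8.3.2).
- Contraception and no-conception period: 120 days (1.8; 4.1, criteria 13 and 14; 4.2, criterion 16).
- End of Treatment visit: day 14 ± 2 (3.9).
- First long-term follow-up call: 3 months ± 2 weeks after that visit (3.9).
- End of study: all subjects have completed the first long-term follow-up interval, withdrawn or died (3.9, 3.11).
- Predicted human half-life: 4 to 6 days (1.5).
- Assumptions: 3 months = 91 days; no new anticancer therapy brings the End of Treatment visit forward.

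**Size of the gap**
- 120 − 60 = 60 days (days 61 to 120).
- 60 / 120 = 50% of the precautionary period.

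**Timing of the first long-term follow-up call**
- Nominal: 14 + 91 = day 105.
- Earliest: 12 + 91 − 14 = day 89.
- Latest: 16 + 91 + 14 = day 121.
- Nominal call to the end of the period: 120 − 105 = 15 days.

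**Coverage under each reading**

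| Days after last dose | Explicit limit | General duty during the study | Scheduled detection |
|---|---|---|---|
| 0–60 | covered | covered | last test at about day 14 |
| 61 to about 105 | not covered | arguably covered while the study runs | none until the call, which has no pregnancy item |
| about 105–120 | not covered | may have ended for the last subject | none |

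For the last subject in the study, the days from the first follow-up call to day 120 may fall under neither duty.

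**Remaining drug at day 60**
- Half-life 6 days: 60 / 6 = 10 half-lives; 0.5^10 = 0.098% remaining.
- Half-life 4 days: 60 / 4 = 15 half-lives; 0.5^15 = 0.003% remaining.

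**After the change:** with a 120-day reporting limit, the gap is 120 − 120 = 0 days.

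**The case against.** The strongest case is that the two windows do different jobs. Contraception carries a safety margin, while reporting targets pregnancies with possible exposure. The protocol is graded: adverse event collection ends at about 30 days, pregnancy reporting at 60, contraception at 120. After 60 days the predicted residual drug is about 0.1% or less. This stands as a limit on the importance of the point: the gap is not evidence of late exposure.

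Second, the two sentences in 8.3.2 can be read together as a mandatory minimum plus a general duty, since the text never says that later pregnancies need not be reported. That reading is available. So is the reading that the 60-day sentence defines the duty, and section 8.3 gives only the number. That sites would in fact diverge is a possibility, not something the documents show.

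Third, 8.3.2 refers to when a pregnancy occurs, so a conception by day 60 that is recognised later is still covered there. This narrows the affected group to conceptions after day 60, although the wording of 8.3 is less clear.

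Fourth, a birth defect is a serious adverse event (8.1.4) and must be reported late if judged reasonably associated with treatment (8.2). This safeguard is partial. Normal outcomes, losses and outcomes judged unrelated have no clear route.

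Finally, the SAE completion guidelines to which 8.3.2 refers are not available here and may already give fuller instructions.

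**Conclusion.** The concern holds. The explicit reporting limit covers half of the sponsor's own 120-day precautionary period, the difference is unexplained, and the text does not settle whether the limit or the general duty governs. A site following the number need not report or follow a pregnancy beginning on days 61 to 120.

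The practical size is small. The subjects have advanced cancer, those of childbearing potential must use contraception, Cohorts A and C were stopped for futility, and Cohort B closed to enrolment after 8 patients. The window can still apply, because section 3.9 allows subjects to stay on treatment after the primary analysis cut-off. No endpoint, error rate or analysis is affected. The timing of the follow-up call rests on the 91-day assumption, and the exposure figures rest on a half-life predicted from monkey data. This should be corrected as an inexpensive improvement in safety capture.

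**What to change.** 1. Change 60 to 120 days in both 8.3 and 8.3.2, for subjects and partners, and state that this is the governing limit. Check the SAE completion guidelines and align them where they differ.
2. Add one question on pregnancy in the subject or partner to the first long-term follow-up call, at about day 105.
3. At the Safety Follow-up visit (day 30 ± 5), ask subjects to tell the site of any pregnancy up to day 120. This covers the 15 days after a nominal call, and up to 120 − 89 = 31 days after the earliest permitted one.

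The cost is two numbers in the safety section, any matching edit to the guidelines, one question in a call that already takes place, and one reminder at an existing visit. No new visit, test or sample is needed. The change requires a protocol amendment, which under section 11.0 may go to ethics committees and authorities, so it is best carried with the next one. The downside is slightly longer reporting for a few cases. If the sponsor prefers to keep 60 days, the protocol should say why that is enough and which of the two duties in 8.3.2 applies afterwards.
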